4.4 Patient Withdrawal After Randomization

The randomization procedure will be performed before laboratory test results are available. In case of significant abnormalities that in the Investigator's opinion interfere with the patient's participation in the study, the patient should be withdrawn from the study.

5 STUDY DRUG

5.1 Study Drug Description

Study Drug:	Levopront®
Active substance:	Levodropropizine
Pharmacological Group:	Antitussive drug with peripheral action
Pharmaceutical form and composition:	syrup 30 mg/5 mL Active substance: Levodropropizine Excipients: Saccharose, Methyl-p-hydroxybenzoate, Propyl-p-hydroxybenzoate, Monohydrate citric acid, Sodium hydroxide, Cherry flavour, Purified water
Presentation:	Package 220 ml brown glass bottle containing 200 ml of solution and closed with an HDPE child-proof cap, complete with an LDPE seal and a PP measuring cap.
Daily dose	180 mg or 30 mL
Dosing regimen:	Orally 10 mL (60 mg) t.i.d. at intervals of at least 6 hours, between meals
Storage conditions:	Keep in a place, out of reach of children Keep at a temperature below 25° C
Manufacturer:	Dompe farmaceutici S.p.A. (Italy)

Comparator product::	Libexin®
Active substance:	Prenoxdiazine
Pharmacological Group:	Antitussive drug with peripheral action
Pharmaceutical form and composition:	100 mg tablets Active substance: prenoxdiazine hydrochloride - 100 mg. Other ingredients: glycerol (glycerin), magnesium stearate, talc, povidone, corn starch, lactose monohydrate.
Presentation:	20 tablets in a blister, one blister per 1 carton
Daily dose	300 mg
Dosing regimen:	orally 1 tablet (100 mg) 3 times a day, no chewing
Storage conditions:	Keep at a temperature below 25° C Keep in a place, out of reach of children
Manufacturer:	Chinoi Pharmaceutical and Chemical Works Private CJSC (Hungary)

NB: Libexin® Prescribing Information are reported in Appendix 1

5.2 Administration of the Study Drug and Randomization

At Visit 1, Day 1 all patients complying with selection criteria will be randomized into one of the two study groups at 1:1 ratio using an Interactive Web-Response System (IWRS):

- The group receiving the study drug Levopront®, syrup 30 mg/5 mL - 92 patients
- The group, receiving reference drug Libexin®, tablets 100 mg - 92 patients.

Randomization and the first intake of study drug at the center is carried out after all the procedures for screening and confirmation of the presence of all the inclusion criteria and the absence of criteria for exclusion.

Further, patients will take investigational products three times a day at intervals of not less than 6 hours, between meals.

The investigational product Levopront® syrup is dispensed by a measuring cup.

Reference drug Libexin®, tablets are swallowed without chewing, with appropriate amount of drinking water at room temperature (200-250 mL).

Overall duration of treatment with the study drug within the study treatment will take 7 days ± 1 day.

5.3 Treatment Compliance

The first dose of the study drug should be taken by patient at the study site under Investigator's control (Visit 1, Day 1). Compliance with guidelines on self-administration of study drugs will be checked by Investigator at Visit 2 and 3 based on account of returned study drug with the diary filled in by the patient. It should be strictly monitored that patient takes 30 mL of the study drug or 3 tablets of reference drug daily.

NB: Patients must take the last dose of the study drug in the evening before Visit 3 (i.e. in the evening of Day 7(±1)) because the **patients should submitted to the examinations requested by the protocol for Day 8 (±1) without having taken the study drug.**

Compliance with the test drug treatment Levopront® will be assessed by the Investigator at Visits 2 and 3. All study sites will be provided with certificated scales. The bottles with syrup will be weighted at the study sites before and after dispensing. The Investigator will measure the difference between initial and final weight. The density of Levopront® is known (indicated in IP documentation), after that calculation of compliance for the syrup will be calculated according to the following formula:

$$\text{Compliance (ml)} = \frac{(\text{m disp.} - \text{m return.})}{\rho \text{ (g/ml)} * V \text{ calc. (ml)}} \times 100\%$$

where m disp. = the m (g) of dispensed syrup, m (g) return. = the number of returned syrup, ρ (g/ml) - density, V (ml) calc. = calculated ml of syrup that the patient had to take from the time of previous visit.

Calculation of compliance for the reference drug will be calculated according to the following formula:

$$\text{Compliance} = (\text{N disp.} - \text{N return.}) / \text{N calc.} \times 100\%$$

where N disp. = the number of dispensed tablets, N return. = the number of returned tablets, N calc. = calculated number of tablets that the patient had to take from the time of previous visit.

Patient compliance for each drug should be similar and be within the interval of 80% to 120%. In case of need patient should be additionally instructed to take the drug.

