5.5 Storage and Account of the Study Drug

Investigator will be responsible for ensuring adequate acceptance, storage, distribution and return of the study drug, as well as keeping records of its account and registration in IWRS.

Limited access and suitable temperature regimen should be ensured. Temperature control should be performed using thermometers, registering minimum and maximum temperature in the

reporting period. Information of temperature monitoring should be regularly included into the temperature monitoring log every day at least two times a day.

Patients will be instructed to return to the study site bottles with the study drug or blisters with reference drug at Visit 2 (Day 4) to assess patient compliance. If the study drugs are lost by the patient a corresponding record should be made in the source documentation and in the study drug log. At the end of the trial after final calculation the study drugs should be returned to Sponsor or to its representative.

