6.13 Early Withdrawal of Patients from the Study or Discontinuation of Study Treatment

The patient has the right to refuse to take part in the study at any stage without giving reasons.

The patient should be withdrawn from the clinical study if:

- Investigator considers it important from the medical point of view
- Patient withdraws his consent
- Patient does not comply with the study drug dosing regimen or study related procedures
- AE or SAE which may impact safety or well-being of patient
- Infection of lower respiratory tract
- Patient is included into the study with violation of inclusion/exclusion criteria

In the following cases immediate discontinuation of the study drug is required:

- Patient starts administration of another study drug
- Pregnancy in a study subject
- Significant protocol deviations that may impact patient's safety and integrity of the study data
- Use of prohibited drugs

If possible, the Investigator should discuss the need to withdraw the patient with the Medical Monitor or inform about patient withdrawal from the study within 48 hours. The reason for patient withdrawal should be specified in the source documents and in CRF. If a patient discontinues from the study for more than one reason, only the main reason should be specified. If a patient withdraws consent because of AE or SAE, the AE or SAE should be specified as the reason for patient withdrawal.

Besides, the Sponsor may terminate the study at any time. The Investigator has the right to terminate the study at any time for medical or regulatory reasons. Study may only be terminated after mutual consultations between the Investigator and the Sponsor.

If the study is terminated early, all patients should undergo procedures of early termination and all study materials should be returned to the Sponsor or his/her representative.

Follow up of AEs, SAEs and pregnancy ongoing at the time of study termination should be continued per protocol if not agreed otherwise between the Investigator and the Sponsor.

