#### **7.3.3 Compliance**

Patient's compliance will be described by treatment groups.

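### The compliance formulas in Protocol 5.3 score recorded losses of study drug as drug taken, so the percentage set against the 80 to 120% band can only be too high for those patients (minor)

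*Protocol*

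**What the plan says.** Protocol 5.3 gives one formula per drug. For the tablets the numerator is dispensed minus returned, "where N disp. = the number of dispensed tablets, N return. = the number of returned tablets", and the denominator is the number due, "N calc. = calculated number of tablets that the patient had to take from the time of previous visit". For the syrup the bottles are weighed: "The Investigator will measure the difference between initial and final weight". That difference is divided by density times the millilitres due. The amount due follows from the daily requirement: "It should be strictly monitored that patient takes 30 mL of the study drug or 3 tablets of reference drug daily". The result is held against a band: "Patient compliance for each drug should be similar and be within the interval of 80% to 120" per cent. The only action that 5.3 attaches to the result is further instruction of the patient when needed. The same section says that the investigator's check uses the returned drug together with the patient's diary.

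Protocol 5.5 foresees loss: "If the study drugs are lost by the patient a corresponding record should be made in the source documentation", and also in the drug log. It does not carry that record into the calculation.

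SAP 7.3.3 says only that "Patient's compliance will be described by treatment groups". Table 9.31 summarises one compliance figure per arm (N, mean, SD, median, range) and gives no derivation.

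**The concern.** Dispensed minus returned equals drug taken plus drug lost. The plan collects the second quantity under 5.5 and then leaves it in the numerator as if it had been taken. The percentage can therefore mislead in two ways. A patient who missed doses and also lost drug can appear compliant, and a patient who took every dose and lost some of the remainder can appear to have over-used. Both drugs are affected, because a weight difference treats missing syrup just as a count treats missing tablets. At stake are the reading against the 80 to 120% band, the decision to re-instruct a patient, and the summary by arm in Table 9.31. The point concerns the numerator only. How many doses are due by a given visit is a separate matter.

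**Working it through.** The plan states no figure to reproduce, since the band is a chosen limit. The check applies the 5.3 formulas to patients whose true intake is known.

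**Inputs from the documents**
- Daily amount due: 3 tablets or 30 mL (Protocol 5.3).
- Pack sizes: 20 tablets per blister, 200 mL per bottle (Protocol 5.1).
- Visit 2 on Day 4, window ±1 day (Protocol Table 1).
- Treatment of 7 days, ±1 day (Protocol 5.2).
- Band: 80 to 120% (Protocol 5.3).

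**Assumptions**
- Three full days are due at Visit 2, that is 9 tablets or 90 mL. The window gives 2 to 4 days, that is 6 to 12 tablets or 60 to 120 mL.
- One pack is dispensed at Visit 1. This matters only when the pack does not come back.
- The documents give no loss rate, so the cases below are illustrations, not expected frequencies.

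**Formula**

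Scored compliance = (dispensed − returned) / due = (taken + lost) / due.

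True compliance = taken / due.

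Error = lost / due, which is never negative.

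**Visit 2, 9 tablets due, 20 dispensed**

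| Taken | Lost | Returned | Scored | True |
|---|---|---|---|---|
| 9 | 1 | 10 | 10/9 = 111.1% | 100% |
| 9 | 2 | 9 | 11/9 = 122.2% | 100% |
| 7 | 1 | 12 | 8/9 = 88.9% | 7/9 = 77.8% |
| 7 | 2 | 11 | 9/9 = 100.0% | 77.8% |
| any | blister not returned | 0 | 20/9 = 222.2% | unknown |

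For the syrup with 90 mL due, the 120% limit is 1.2 × 90 = 108 mL, so a full taker leaves the band after losing more than 18 mL. With 20 mL lost, a patient who took 90 mL scores 110/90 = 122.2%, and one who took 70 mL (77.8%) scores 90/90 = 100.0%.

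**Across the Visit 2 window**
- 6 tablets due: two lost give 8/6 = 133.3%; the syrup limit is 0.2 × 60 = 12 mL; an unreturned blister gives 20/6 = 333.3%.
- 12 tablets due: three lost give 15/12 = 125.0%; the syrup limit is 0.2 × 120 = 24 mL; an unreturned blister gives 20/12 = 166.7%.

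**Whole treatment, 21 tablets or 210 mL due**
- Full taker, four lost: 25/21 = 119.0%, inside the band. Five lost: 26/21 = 123.8%, outside.
- Syrup limit: 0.2 × 210 = 42 mL.
- At the lower limit one tablet is enough: 16 taken and one lost gives 17/21 = 81.0% against a true 16/21 = 76.2%.

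**With documented loss subtracted** (9 due)
- 9 taken, 2 lost: (20 − 9 − 2)/9 = 100.0%.
- 7 taken, 2 lost: (20 − 11 − 2)/9 = 77.8%.

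Both agree with true intake.

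**The case against.** The best defence is that the formula is not the whole assessment. Section 5.3 has the investigator read the drug account together with the diary, the diary records intake (6.10), and 5.5 puts a loss record in the same file. An investigator with all three would see that 222% is a missing blister. Section 9.6 also reports daily and total doses by arm, so the percentage is not the only numerical view of dosing. This stands, and it limits the harm. It does not repair the formula: no text says how a disagreement between count and diary is resolved, or that the percentage is corrected, so sites could treat the same case differently.

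It is also fair that the Visit 2 cases are the most sensitive ones. Table 9.31 has a single block with no split by visit, and over 21 doses a full taker needs five lost tablets or more than 42 mL to leave the band at the top. For tablets supplied in a blister, the loss of two or three single tablets is an assumed event.

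Three stronger readings are tempting, and the documents do not support them.
- A reader might infer that a wrong percentage moves patients into or out of the per-protocol set. Protocol 9.4.1 and SAP 5.1 define compliant as free of serious protocol deviations, to be settled before database lock. Section 6.13 lists "Patient does not comply with the study drug dosing regimen or study related procedures" as a ground for withdrawal. None of these names the 80 to 120% band.
- A reader might infer that spills and residue in the measuring cup inflate the syrup arm more than the tablet arm. Section 5.5 speaks only of lost drug and requires no spill record, neither section says what happens to residue, and tablets can be dropped too.
- A reader might infer that a falsely high percentage would count as an overdose under 6.12.8. That section does mention an allowance of 120% compliance, but it defines overdose by the amount administered on a treatment day and does not say that the figure for a visit interval is used.

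**Conclusion.** The rule is wrong as written, and the consequence is minor. For any patient with lost or unreturned drug, the 5.3 percentage is too high by lost/due. With 9 doses due at Visit 2, two lost tablets turn 100% into 122% and 78% into 100%; over the whole course each lost tablet adds 1/21 = 4.8 points. The sizes rest on the assumed number of doses due (6 to 12 within the Visit 2 window) and, for an unreturned pack, on one blister having been dispensed. The direction rests only on the formula.

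What is affected is the reading against the band, the prompt to re-instruct, and Table 9.31. An effect on the per-protocol set, the primary comparison or the difference between arms is not shown, and without a loss rate its size cannot be estimated.

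**What to change.** In Protocol 5.3 and SAP 7.3.3, define amount taken as dispensed minus returned minus the loss documented under 5.5, for both drugs. Where a container is not returned, set the count-based value to missing and show the diary-based value, flagged as such. Use the corrected figure for the 80 to 120% check and in Table 9.31.

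Apply the rule identically to both arms and both parts of the study. Because results of the first part are already known (Protocol 3.2), report its compliance values both with and without the correction.

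The cost is one line in each document and a small re-derivation from drug logs and diaries that are already kept. The downside is that, for the affected patients, the figure rests on the patient's own report of the loss or on the diary, which in an open-label trial cannot be verified independently. The flag keeps those values visible.

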5.4 Packaging and labeling of the study drug

The study drug will be provided by Sponsor. The study drug will be packed and labeled according to the current legislation and applicable requirements, in particular, Federal Law of the Russian Federation of April 12, 2010 No 61 FZ On Drug Circulation, current edition.¹⁷

Labeling of the study drugs is shown in Figure 2, 3.

Figure 2. Draft Label of the Study Drug, Trial LDP014

For clinical trial only
 
Clinical trial N° LDP0114
 
Patient n° □□-□□
 
Visit No _____ KIT XXX*
 
Levopront (Levodropropizine), syrup 30 mg/5 mL - 200 ml for oral use
 
Dosage: Take 10 mL three times per day. between food intakes
 
Keep in a dry, dark place at a temperature below 25° C
 
Manufacturer Dompe Farmaceutici S.p.A. (Italy);
 
Study sponsor Dompé farmaceutici S.p.A.
 
Local contact: IPHARMA LLC Russia, tel. + 7 [contact]
 
Date dispensed _____
 
Batch: XXXXXX Expiry date: XXXXXXXX
 
Keep out of reach of children

Figure 3. Draft Label of Reference Drug, Trial LDP0114

For clinical trial only
 
Clinical trial N° LDP0114
 
Patient n° □□-□□
 
Visit No _____ KIT XXX*
 
Dosage: Take 1 tablet 3 times per day
 
Date dispensed _____

5.5 Storage and Account of the Study Drug

Investigator will be responsible for ensuring adequate acceptance, storage, distribution and return of the study drug, as well as keeping records of its account and registration in IWRS.

Limited access and suitable temperature regimen should be ensured. Temperature control should be performed using thermometers, registering minimum and maximum temperature in the

reporting period. Information of temperature monitoring should be regularly included into the temperature monitoring log every day at least two times a day.

Patients will be instructed to return to the study site bottles with the study drug or blisters with reference drug at Visit 2 (Day 4) to assess patient compliance. If the study drugs are lost by the patient a corresponding record should be made in the source documentation and in the study drug log. At the end of the trial after final calculation the study drugs should be returned to Sponsor or to its representative.

5.6 Concomitant Therapy

Patients may receive symptomatic treatment of the main disease.

For allowed symptomatic treatment are permitted antipyretics - NSAIDs: Paracetamol (maximum single dose of 2 g, the maximum daily dose of 4 g); ibuprofen (200 mg 3-4 times a day), acetylsalicylic acid (a single dose of 0.5-1 g, maximum single dose of 1 g, the intervals between doses of the drug for at least 4 hours, the maximum daily dose of 3 g). To improve nasal breathing may be used vasoconstrictor nasal drops and sprays. In case of appearing of any symptoms of laryngotracheitis it is permitted to use local antiseptics.

The decision on the appointment of concomitant therapy in each case takes the Investigator.

All basic and concomitant drugs, including food supplements (FS) should be recorded in the source documents and in Case Report Form (CRF). It includes all drugs and food supplements except the study therapy taken by patients within three months before screening and at any time during the clinical trial. Name (predominantly name of the active substance), dosage, frequency of dosing, route of administration, indications for use (including underlying disease, concomitant conditions, adverse events or prevention), dates of start and completion of the study drug intake should be reflected in the source documentation and in CRF. If study therapy intake was ongoing at the time of study completion, an appropriate remark should be made in the CRF.

5.7 Prohibited Concomitant Therapy

During the study treatment with other investigational products and drugs listed below is not permitted:

- Expectorant drugs (Farfara, violet, licorice, marjoram, inula, hormopsis, polygala, althea, herpinhydrate, lycorine, ether oil preparations)
- Mucolytics: enzymes (trypsin, chemotrypsin, ribonuclease), sulfur-containing compounds (acetylcysteine, carbocysteine), vasicine alkaloid derivatives (bromhexine, ambroxol)
- Antitussive agents of central and peripheral action, expect the study IMPs provided for by the study
- Antibiotics
- Combined "anti-commoncold" drugs
- Antihistamines
- Drugs that have a sedative effect and reinforcing the depressive effect on the central nervous system, as well as other cough suppressants, except for the study drugs.
- Antiviral drugs (except Arbidol®)

5.8 Patient Nutrition and Activity Limitations

Patients should maintain usual diet and limit physical exercise, refrain from alcohol and smoking for the whole period of the study.

For the whole duration of the study, subjects must agree to use adequate contraception measures.

Adequate birth control measures include:

- oral or transdermal contraceptives,
- condom or diaphragm (barrier method) with spermicide or
- intrauterine device.

6 DESCRIPTION OF PROCEDURES

All study procedures will be performed according to the requirements and recommendations of the Good Clinical Practice guidelines of International Conference for Harmonization (ICH GCP) and Eurasian Economic Union (EAEU), principals outlined in the Declaration of Helsinki, as well as according to the current legislation and applicable regulations of Russian Federation. The Investigator must consent to accept monitoring, audits and inspections at the clinical site and provide direct access to the study materials to the Sponsor and its representatives, Independent Ethics Committee and regulatory authorities.

6.1 Informed Consent

Informed consent will be obtained at screening before any study-related procedures are made.

6.2 Patient Registration

Each patient signing Patient Information Leaflet and Informed Consent Form will be assigned an individual registration number consisting of four digits: □□-□□ - the first two digits denote the site number, the last two digits – the number of patient at the site (01, 02, 03 etc.). Guidelines for patient registration in the IWRS will be provided to the Investigator before the study.

6.3 Demographic Data and Medical History

To assess patient compliance to inclusion/non-inclusion criteria, patient demographic data (sex, date of birth/age, race) and full medical history, including significant acute and chronic disorders and conditions (e.g. menopause), surgical interventions and allergic reactions should be collected. Besides, patient should be asked about hospitalizations and/or surgical interventions scheduled within the study period (if applicable). All new diagnoses and conditions detected at screening (including results of laboratory and instrumental studies) should be attributed to the patient's medical history.

History of smoking is assessed by the pack/year index according to the following formula:

$$\text{Pack/year index} = \frac{\text{No. of cigarettes per day} \times \text{Smoking experience (years)}}{20}$$

6.4 Physical Examination

Physical examination includes assessment of general appearance, condition of skin, mucous membranes, neck (including thyroid gland), eyes, ears, nasopharynx, lungs, heart, abdomen, lymph nodes and neurological status.

Changes versus baseline characteristics, determined to be AEs should be appropriately reported in the source documentation and in CRF.

